6.1.5 Handling of missing and/or incomplete data

Patients will be missing specific data points for a variety of reasons. With the exception of validated instruments, missing values for a given time point will not be imputed and analyses will be conducted using an observed case approach. For validated instruments, missing items will be handled according to instructions from the relevant scoring manuals. Missing dates will be handled with an observed case approach.

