4.2.1 Data collection schedule

Table 5 describes expected follow-up. Follow-up visits will be scheduled between 48-72 hours after hospital discharge, 10-14 days after enrollment (end of treatment visit, both periods), and 44 days after enrollment (both periods). 48-72 hours after hospital discharge, both pre- and post-period patients will be called via telephone. A limited physical visit will be conducted 10-14 days after enrollment. However, for subjects unable to be seen back at the site, a telephone interview will suffice. Research data will be collected through follow-up visits at between days 10-14 through an in-person visit (end of treatment visit; if patient cannot be seen back at site, telephone call can occur up to 21 days from enrollment) and at 44 days (telephone call can occur up to 51 days from enrollment), through a telephone interview of the subject in both the pre- and post-periods. Additionally, electronic medical chart data will be reviewed at the 10-14 day and 44 day time points from enrollment. Any additional visits to the visit schedule below will be at the discretion of the subject and treating physician.

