6.2 Handling of missing data

The SAP will define how missing values and information from subjects lost to follow-up will be handled. Site procedures will be developed to minimize the amount of missing data however, as this is a pragmatic trial, missing data is expected. Certain outcomes are based on data availability from sites (e.g. laboratory values will be summarized for subjects who had data collected).

The extent of missing values will be examined to assess completeness of data among the study cohort. In addition, the characteristics of participants with and without missing data will be examined to assess whether participant characteristics have any relationship to incompleteness.

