6.1.3 Rounding

Means and medians will be rounded to one decimal more than that which the variable was recorded. Standard deviations will be rounded to two decimals more than that which the variable was recorded.

Percentages will be rounded to the nearest integer. Percentages for responses to a variable will only include patients with non-missing data, i.e. the denominator will be the number of patients with non-missing data.

P-values will be reported to three decimal places. Probabilities that are <0.001 will be presented as " <0.001 ."

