6.2 Statistical Methods

Descriptive analyses will be performed as follows: for continuous variables, patient counts, percentages, means, 95% confidence intervals (CI) of the means, standard deviations (SD), medians, first (25th percentile) and third (75th percentile) quartiles, minima and maxima, and number missing (where applicable) will be reported. For categorical variables, patient counts and percentages for each category, as well as number missing (where applicable), will be reported. Where applicable, summaries for continuous variables will include frequencies and percentages for discrete categories (e.g., number of ED visits: 0, 1, 2, and so forth).

For applicable categorical variables of baseline characteristics (including demographics, infection characteristics at baseline and the day 10-14 follow-up visit, comorbid conditions reported at baseline, and prior healthcare resource utilization within past 3 months), the pre-period will be compared with the post-period using chi-square tests or Fisher's exact tests, as appropriate. Differences in proportions of the pre-period and post-period and their corresponding asymptotic 95% confidence interval (CI) will be reported, where applicable. For applicable continuous variables, two-sided Student's t-tests and Mann-Whitney U tests will be used where normality assumptions have, and have not, been met, respectively. Where applicable, differences in descriptive statistics, proportions, and corresponding 95% CI will also be provided between the pre- and post-periods.

Hypothesis testing is specified for outcomes in Section 6.2.4. All statistical testing, if done, will be at the significance level of 0.05. Other outcomes will be analyzed by descriptive analyses and by number of incidences where applicable. Planned analyses are presented in Section 6.2.4.2 for secondary

outcomes. All planned hypothesis testing and any unplanned deviation from hypothesis testing for secondary outcomes will be purely exploratory, as adequate power will not be present to determine statistical significance. There will be no adjustments made for multiple comparisons.

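### The SAP text omits the protocol's comparison of patients with and without missing data, and it gives two conflicting rules for patients whose day 10-14 response cannot be assessed

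*SAP*

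**What the plan says.** **Protocol 6.2** says that "as this is a pragmatic trial, missing data is expected" and leaves the handling of missing values to the SAP. It also makes two commitments of its own. The first is "The extent of missing values will be examined to assess completeness of data among the study cohort". The second is that "the characteristics of participants with and without missing data will be examined to assess whether participant characteristics have any relationship to incompleteness".

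**SAP 6.1.5** sets the rule: "missing values for a given time point will not be imputed and analyses will be conducted using an observed case approach". Validated instruments are exempt, for missing items only. For percentages, SAP 6.1.3 adds that "the denominator will be the number of patients with non-missing data".

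**SAP 6.2** keeps the protocol's first commitment in part. For categorical variables, patient counts and percentages, "as well as number missing (where applicable), will be reported", with similar wording for continuous variables. The second commitment appears neither in the methods of SAP 6.1.5 and 6.2 nor in the outputs of SAP 7.0. SAP 5.0, which declares changes from the protocol's analyses, covers laboratory-derived characteristics and the choice of tests but not this.

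**Visit design.** Protocol 4.2.1 plans a physical visit at day 10-14, but "for subjects unable to be seen back at the site, a telephone interview will suffice", by telephone up to day 21. Protocol Appendix 11.1 has lesions measured at enrollment and at physical follow-up visits.

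**Response.** SAP Appendix B separates complete from partial response by whether the lesion shrank or kept its size. All remaining patients are failures. There is no missing category.

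**The concern.** A patient reached only by telephone at day 10-14 has been followed up as the protocol allows, but has no lesion area and so no assessable response. Under the observed-case rule that patient leaves the response comparison, which is then confined to those who came back.

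The groups are sequential and not randomized, so nothing in the design balances attendance between multi-day usual care and a single infusion. The comparison promised in Protocol 6.2 is the trial's own check on whether the missing patients differ, and it is not in the SAP.

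The conflict in Appendix B adds to this. Two programmers following different sections would put the same patient in different places: one excludes the patient, the other counts a failure, even if the patient reports being well by telephone. Response is the clinical check that a shorter stay is not accompanied by a poorer outcome, so its denominator should not rest on an unstated choice.

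**Working it through.** **1. The plan's own figures.** Protocol 6.3 gives SD 3.0 days, difference 2 days, two-sided alpha 0.05 and 80% power. The normal approximation is n = 2 × (1.960 + 0.842)² / (2/3)² = 35.3, so 36 per period. The t-test version gives 36.3, so 37, the stated figure. Going from 37 to 43 implies attrition of 1 − 37/43 = 14.0%. That is an allowance for the length-of-stay comparison, not a day 10-14 non-attendance rate. The documents give no attendance or response rate, so every rate below is assumed.

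**2. Observed-case bias within one period.** Let p be true response, a the attendance of responders and b the attendance of non-responders. The observed rate is pa / [pa + (1 − p)b].

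| p | a | b | Observed | Bias (points) |
|---|---|---|---|---|
| 80% | 86% | 86% | 80.0% | 0 |
| 90% | 90% | 70% | 92.0% | +2.0 |
| 85% | 90% | 70% | 87.9% | +2.9 |
| 80% | 95% | 50% | 88.4% | +8.4 |

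The bias is zero when a = b. If both periods share the same p, a and b, it cancels in the difference. If the first row described one period and the last row the other, the observed difference would be 8.4 points with no true difference.

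**3. The two SAP rules on the same data.** Assume 3 of 43 missing in the pre-period and 9 of 43 in the post-period, with about 85% response among those seen (34 of 40 and 29 of 34).

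| Rule | Pre | Post | Post − pre |
|---|---|---|---|
| Observed case (6.1.3, 6.1.5) | 34/40 = 85.0% | 29/34 = 85.3% | +0.3 |
| Closing branch of Appendix B | 34/43 = 79.1% | 29/43 = 67.4% | −11.6 |

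Best/worst-case limits for this example run from (29 − 37)/43 = −18.6 points to (38 − 34)/43 = +9.3 points.

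**4. Neither rule is safe by default.** Assume response of 90% in patients seen and 60% in those not seen, with 5% and 25% not seen.
- True rates: 0.95 × 0.90 + 0.05 × 0.60 = 88.5% and 0.75 × 0.90 + 0.25 × 0.60 = 82.5%, a difference of −6 points.
- Observed case: 90% and 90%, a difference of 0.
- Missing as failure: 0.95 × 0.90 = 85.5% and 0.75 × 0.90 = 67.5%, a difference of −18.

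One rule hides the assumed difference and the other exaggerates it.

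**5. Bounds at the implied 14%.** With 6 of 43 missing and 31 of 37 responding (83.8%), that period's rate lies between 31/43 = 72.1% and 37/43 = 86.0%.

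**The case against.** The case against has five parts.

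- **Delegation.** Protocol 6.2 hands missing-data handling to the SAP, so the observed-case rule is not itself a departure, and silence in the SAP need not cancel the protocol's comparison. This stands as far as it goes. But the comparison is a separate commitment, and an analysis without a method or an output is unlikely to be produced. SAP 7.0 lists only potential outputs, and the table shells and some SAP sections are not in the text available, so absence is judged on the methods, the output list and section 5.0.
- **Visibility.** A reader might infer that bias would go unseen. That is too strong: missing counts are to be reported and disposition is tabulated, so the amount missing in each period would show. What is lost is whether the missing patients differ.
- **Existing sensitivity output.** SAP 6.2.4.1 repeats the primary outcome for study completers, and Appendix B extends the flag to certain secondary outcomes. This does not address the gap: a patient interviewed by telephone at both time points can be a completer without a lesion measurement.
- **Scope.** A reader might extend the point to pain and SF-12. Both are patient-reported and may be obtainable by telephone. SAP 4.3 labels SF-12 as in person, which is a separate inconsistency to reconcile.
- **Speculation and proportion.** The visit schedule and the return-or-telephone inclusion criterion are the same in both periods, and no passage shows that attendance differs. Secondary tests are exploratory under SAP 6.2. Both points stand, and they limit the size of the claim. Multiple imputation or weighting on several covariates, with about 43 patients per period, is not called for.

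**Conclusion.** The point holds in a limited form. A protocol commitment has no counterpart in the available SAP text and its removal is not declared. The SAP also contradicts itself on how a missing response is classified.

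The documents do not show that the response comparison is biased. They show that it can be, if attendance is related to outcome and differs between periods, and that the check meant to address this is not planned. Under the assumed attendance patterns the observed rate in a period is 0 to 8.4 points too high. The choice between the two SAP rules alone can move the between-period difference from about 0 to about −12 points (3 versus 9 of 43 missing, about 85% response among those seen). With equal numbers missing and equal response among those seen, the two rules give the same difference of zero.

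The effect is confined to lesion area, other examination findings, and response. Length of stay does not depend on this visit, so the primary conclusion is not at risk. The change should be made because it is cheap and decides what the response comparison can support.

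**What to change.** 1. **SAP 6.1.5 and 7.0:** add a table, by period, of key baseline characteristics (for example lesion area, infection type, SIRS, Charlson index) for patients with and without an in-person day 10-14 assessment. Add counts by contact mode (in person, telephone, none) where the mode is recorded. If the sponsor decides against the comparison, list its removal with a reason in SAP 5.0.
2. **SAP Appendix B:** reconcile the response derivation with 6.1.3 and 6.1.5. Give response an explicit missing category, assigned before the closing branch, so that failure is reserved for patients who were assessed.
3. **SAP 6.2.4.2:** report response as observed case, with a missing-as-failure analysis and best/worst-case bounds as sensitivity analyses.

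**Cost:** one extra table, a short change to one derivation, and two simple reruns of the response table. The planned sample size does not change. Some table cells will be small, and the bounds will be wide for an exploratory outcome. Counts by contact mode depend on the CRF recording it, which the available text does not confirm.

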6.1.6 Interim analysis

As documented in the protocol, Version 6.0, there was an interim analysis of data to check the sample size assumptions based on approximately 25 enrolled pre-period patients. A separate report was completed on the interim analysis. No further interim analysis is planned. The output that was produced for the interim analysis is denoted in the table shells with a J following the title.

6.1.7 Subgroup analyses

Currently no subgroup analyses are planned for this study. If applicable, analyses will be repeated for subgroups of interest.

6.1.8 Statistical software

All analyses will be performed by statisticians/data analysts, in accordance with Good Programming Practices guidelines, and will follow the statistical analysis plan outlined in this document, including the corresponding table shells referenced herein. All analyses will be performed using [REDACTED] or later to format tables and listings. Table, listing and figure output will be generated and delivered as Adobe Acrobat (PDF) files.

6.1.9 Quality Control

All output will be validated and/or QC'd according to Mapi standard operating procedures. Output tables and figures will be double programmed and undergo statistical review prior to being sent to Allergan.

6.2 Statistical Methods

Descriptive analyses will be performed as follows: for continuous variables, patient counts, percentages, means, 95% confidence intervals (CI) of the means, standard deviations (SD), medians, first (25th percentile) and third (75th percentile) quartiles, minima and maxima, and number missing (where applicable) will be reported. For categorical variables, patient counts and percentages for each category, as well as number missing (where applicable), will be reported. Where applicable, summaries for continuous variables will include frequencies and percentages for discrete categories (e.g., number of ED visits: 0, 1, 2, and so forth).

For applicable categorical variables of baseline characteristics (including demographics, infection characteristics at baseline and the day 10-14 follow-up visit, comorbid conditions reported at baseline, and prior healthcare resource utilization within past 3 months), the pre-period will be compared with the post-period using chi-square tests or Fisher's exact tests, as appropriate. Differences in proportions of the pre-period and post-period and their corresponding asymptotic 95% confidence interval (CI) will be reported, where applicable. For applicable continuous variables, two-sided Student's t-tests and Mann-Whitney U tests will be used where normality assumptions have, and have not, been met, respectively. Where applicable, differences in descriptive statistics, proportions, and corresponding 95% CI will also be provided between the pre- and post-periods.

Hypothesis testing is specified for outcomes in Section 6.2.4. All statistical testing, if done, will be at the significance level of 0.05. Other outcomes will be analyzed by descriptive analyses and by number of incidences where applicable. Planned analyses are presented in Section 6.2.4.2 for secondary

outcomes. All planned hypothesis testing and any unplanned deviation from hypothesis testing for secondary outcomes will be purely exploratory, as adequate power will not be present to determine statistical significance. There will be no adjustments made for multiple comparisons.

6.2.1 Patient Disposition

The number and percentage of enrolled and FAS patients, number and percentage of patients who complete the study, and number and percentage of patients who discontinue from the study and reason for withdrawal will be summarized in tables for all patients. This information will also be reflected in a data listing including the patient's enrollment date, early discontinuation or study completion date, and date of death, if applicable. Patients who are excluded from the enrolled set due to not meeting inclusion or exclusion eligibility criteria will be summarized in listings.

Although tables and listings will not reflect screen failures captured with enrollment logs, the clinical study report (CSR) text will address the approximate number of screen failures and the most common reasons for screen failure.

6.2.2 Demographic and Baseline Characteristics

All demographic data will be summarized in tables and listings for the enrolled and FAS populations. Descriptive statistics will be summarized for age (in years), height at baseline (in cm), weight at baseline (in kg) and body mass index (BMI) at baseline (in kg/m²). Patient counts and percentages will be summarized for age (e.g., <20 years, 20-29 years, 30-39 years, etc.), race/ethnicity, gender, employment status (e.g., employed, full time, part time, unemployed), admission source (e.g., from home, LTC, SNF, nursing home), and insurance information. This information will be captured in listings with date of birth.

All baseline characteristics for comorbid conditions will be summarized for the FAS population by patient counts and percentages in tables and include the following measures: myocardial infarction, congestive heart failure, peripheral vascular disease, cerebrovascular disease, dementia, chronic obstructive pulmonary disease, connective tissue disease, peptic ulcer disease, mild liver disease, moderate or severe liver disease (Child- Pugh Class B and C), hemiplegia, lymphedema / chronic venous stasis, diabetes mellitus (with and without end-organ damage), moderate to severe chronic kidney disease (e.g., actual measurement and GFR, estimated measurement and GFR, unknown measurement), leukemia and remission status, lymphoma and remission status, metastatic solid tumor and remission status, alcohol abuse, drug abuse including illicit needle use, protein calorie malnutrition, immuno-compromising conditions such as HIV, acquired immune deficiency syndrome (AIDS), receiving ≥20 mg Prednisone daily (or therapeutically equivalent steroid), receiving TNF inhibitors, receiving any other immune modulating medication including biologics, and receiving chemotherapy. The Charlson Comorbidity

Index will be derived and described by descriptive statistics. All data will be reflected in listings.

Healthcare resource utilization within the 3 months prior to study enrollment will be reported in tables for the FAS population. Number of patients and percentages of occurrences (e.g., none, any, 1, 2, ≥ 3) and primary reasons for the following will be reported for hospitalizations, admissions to the ICU, surgical interventions, and ED or outpatient visits. Descriptive statistics will also be presented for these variables. Additionally, number of patients and percentages of coded diagnoses terms will be reported for hospitalizations and admissions to the ICU and number of patients and percentages for specified surgical procedures. The number and percentages of patients with minor and major surgical procedures will be displayed. The table will also reflect the number and percentages of patients with dialysis use, prior medications used for chronic diseases, antibiotics taken within 3 months of study enrollment (any and described by prescription reason and treatment failure and described by prescription reason), and wound care for the presenting infection. Listings for hospitalizations will capture the type of visit, primary reason for visit, primary diagnosis (coded and verbatim), admission date and time, discharge date and time, ICU admissions for hospitalizations, and discharge disposition. Prior antibiotic medications will be reported in a listing and will include start date and end date, medication named (coded and verbatim), reasons for prescription, dose with units and frequencies, route, and reason for discontinuation.

6.2.3 Infection Characteristics at Baseline and Follow-up

Infection characteristics at baseline and the day 10-14 follow-up visit will be reported in tables for the FAS population. As applicable, patient counts and percentages will be summarized for primary infection type, purulent drainage from primary lesion, any pain with primary lesion, tenderness of primary lesion, primary lesion location, primary lesion size ($75\text{cm}^2 - 150\text{cm}^2$, $\geq 150\text{cm}^2$) number of additional lesions (e.g., 0, 1, 2, ≥ 3), fever, SIRS (met i.e., ≥ 2 criteria present, by individual criteria, and by number of criteria met), and recurrent/ABSSSI infection in prior 6 months. Descriptive statistics will be summarized for primary lesion size and pain on a 10-point scale. Differences in infection characteristics between the pre- and post-period will be assessed using statistical significance testing. All of the aforementioned variables will be reflected in listings.

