6.1.2 Sample size

An estimated 86 patients are anticipated to be enrolled at one US site. The sample size was initially estimated for a two-sided hypothesis test (two-sample equal-variance t-test) with a significance level of 0.05 comparing total hospital time (number of days) between the pre- and post-periods with 80% power. Assuming an average hospital length of stay of 4.0 days (inclusive of all enrolled subjects), with a standard deviation of 3.0 days, and a 2 day reduction in length of stay between the pre- and post-periods, it was estimated that 37 subjects in each arm of the trial (total enrollment of 74) would be required to demonstrate a mean reduction in hospital stay of 2 day. The final enrollment, including adjustments for attrition came to 86 subjects (43 patients in each period).

The average length of stay and variance for the site was determined after an estimated 25 subjects were enrolled in the pre-period. The sample size was confirmed with the interim analysis and the enrollment of 86 patients will be targeted.

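### Day 10-14 lesion size and pain score are, on the natural reading of the SAP, tested between two non-randomised periods without using each patient's baseline value

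*SAP*

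**What the plan says.** SAP 6.2.3 reports infection characteristics for the full analysis set at baseline and at day 10-14. On the continuous variables it says: "Descriptive statistics will be summarized for primary lesion size and pain on a 10-point scale". On testing it says: "Differences in infection characteristics between the pre- and post-period will be assessed using statistical significance testing".

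SAP 6.2 supplies the tests. Its paragraph on baseline characteristics includes "infection characteristics at baseline and the day 10-14 follow-up visit" among what is compared between periods. Categorical variables get a chi-square or Fisher's exact test. For the rest: "For applicable continuous variables, two-sided Student's t-tests and Mann-Whitney U tests will be used where normality assumptions have, and have not, been met, respectively". None of these tests takes a covariate.

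SAP 7.0 lists separate tables for baseline (5.1) and day 10-14 (5.2). The only covariate-adjusted model, in SAP 6.2.4.1, is for hospital days. It is motivated there by possible baseline differences between the periods. It offers baseline lesion area in categories as a stepwise candidate and does not list pain.

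**The concern.** At day 10-14, lesion size and pain are measured after treatment has started, so a rule written for describing baseline comparability does not suit them. SAP 3.0 describes the two periods as independent patient groups, and allocation is by calendar time. Recruitment also differs. In Protocol 3.3.1 (pre-period) the coordinator screens, core-team physicians decide flagged cases, and the treating physician is blinded to the enrolment decision. In Protocol 3.3.2 (post-period) the treating physician may apply the checklist and enrol. That could shift the initial severity of enrolled lesions.

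If one period starts with larger or more painful lesions, part of that difference will still be present at day 10-14. The raw test can then show a difference with no treatment effect, or mask a real one. It also leaves unused a measurement that could reduce residual variance. At stake is how Table 5.2 is read by someone asking whether a pathway meant to shorten stay is accompanied by slower healing.

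**Working it through.** **The plan's own figure.** SAP 6.1.2 sizes the trial on hospital days, "with a significance level of 0.05 comparing total hospital time (number of days) between the pre- and post-periods with 80% power", "with a standard deviation of 3.0 days, and a 2 day reduction in length of stay between the pre- and post-periods".

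- Normal approximation: 2 × (1.960 + 0.842)² × (3/2)² = 35.3, so 36 per period.
- Exact noncentral t: 36 gives 79.7% power and 37 gives 80.8%, so 37, as stated.
- The attrition rate is not stated; 1 − 37/43 = 14.0% is implied.

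The figure reproduces and is unaffected by this point. The plan gives no sizing for lesion size or pain.

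**Inputs for the check.** From the SAP: n = 43 per period and two-sided alpha 0.05. Assumed, because the documents do not give them: rho, the within-period correlation between a patient's baseline and day 10-14 value, and d, the systematic baseline difference between periods in SD units. Values are taken as normal with equal SD at both visits, with no true effect. The period difference is assumed to reach day 10-14 only through the baseline value.

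**Bias of the raw comparison.** The raw day 10-14 difference has expectation rho × d SD. Its standard error is √(2/43) = 0.216 SD. The two-sided error rate comes from a noncentral t with 84 degrees of freedom and noncentrality rho × d / 0.216. For rho 0.5 and d 0.3 this is 0.15/0.216 = 0.70, giving 10.6%.

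**Precision.** Adjustment multiplies residual variance by 1 − rho², so the CI width is multiplied by √(1 − rho²). The last column shows what happens to an effect that the raw test detects with 80% power.

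| rho | Raw error, d = 0.3 | Raw error, d = 0.5 | CI width vs raw | Power, from 80% raw |
|---|---|---|---|---|
| 0.1 | 5.2% | 5.6% | 0.995 | 80.4% |
| 0.3 | 7.0% | 10.6% | 0.954 | 83.6% |
| 0.5 | 10.6% | 20.9% | 0.866 | 89.9% |
| 0.7 | 16.1% | 36.1% | 0.714 | 97.5% |

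At 37 measured per period the error rates over rho 0.3-0.7 are 6.7% to 31.8%.

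In these rows d is a systematic difference. Chance imbalance (standard error 0.216 SD at baseline) is already allowed for in the raw test's overall 5%; it costs precision, not error rate.

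**Simulation check** (8,000 runs per setting, 43 per period, ordinary model-based standard errors). For rho 0.3-0.7 and d 0.3-0.5, the raw test agreed with the table and ANCOVA rejected in 4.6-5.1% of runs. A change-score t-test rejected in 7.7-27.5%, so testing change from baseline is not a substitute.

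**If the period difference does not fade.** Suppose the difference persists unchanged to day 14. The raw bias is then d, and the ANCOVA bias is d × (1 − rho). At rho 0.5 that leaves 0.15 SD for d = 0.3 and 0.25 SD for d = 0.5. Simulated error is 12.5% and 24.6% for ANCOVA, against 28% and 64% for the raw test.

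**The case against.** The strongest reply is that little hangs on these tests. Day 10-14 lesion size and pain score are in no list of primary or secondary outcomes, and they sit outside the SAP's outcomes section (6.2.4). SAP 6.2 calls even the testing of secondary outcomes exploratory. No section says that Table 5.2 will be interpreted as a treatment effect. All of this stands and limits the weight of the point.

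A reader might infer that the trial's conclusion on healing rests on raw values. It does not. The tested response outcome (SAP 6.2.4.2, Appendix B) uses within-patient change in pain and lesion area. It is coarse, since any reduction in area meets the size condition for a complete response, and it is compared without covariates. But baseline is not ignored there.

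A reader might also take lesion size and pain to be the only continuous clinical measures tested at this visit. SAP 4.1 lists blood pressure, white cell count, C-reactive protein and others at the same visit, and the SAP 6.2 rule may reach them too.

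The wording leaves some room. In SAP 6.2 the day 10-14 phrase qualifies the categorical variables, and the continuous sentence is limited to those that are applicable. The table shells are not among the documents, so a baseline-adjusted row cannot be ruled out. Still, SAP 6.2.3 tests infection characteristics without exception and names no other method, so the unadjusted reading is the natural one.

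Finally, rho may be low if most lesions and pain have nearly resolved by day 10-14, and a normal model does not represent values piled up at zero. That also stands, which is why rho 0.1 is shown.

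**Conclusion.** The point holds as a modest, low-cost improvement to a supporting analysis. As written, the SAP most naturally compares raw day 10-14 lesion size and pain between non-randomised periods, and no analysis of these two continuous variables conditions on the baseline value already collected.

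The size depends on assumptions the documents cannot settle. A systematic baseline difference of 0.3-0.5 SD takes the false-positive rate from 5% to between 7% and 36% over rho 0.3-0.7, and adjustment narrows the interval by 5-29%. Near rho 0.1 neither matters. The figures take 43 measured patients per period. That is enrolment before attrition, and Protocol 4.2.1 allows a telephone interview in place of the day 10-14 visit, whereas Protocol 11.1 measures lesions at physical visits. As an illustration, with 30 measured per period the effect that has 80% raw power at 43 has 64% raw and 77% adjusted at rho 0.5.

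It is tempting to conclude that ANCOVA restores a 5% error rate. That is true only if the period difference acts through the measured baseline value. If it persists to day 14, or if calendar time confounds the comparison in other ways, adjustment reduces the bias without removing it. The documents do not say which pattern applies.

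**What to change.** In SAP 6.2, SAP 6.2.3 and Table 5.2:

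- Take day 10-14 lesion size and pain score out of the test rule for baseline characteristics.
- Estimate the between-period difference for each by ANCOVA: day 10-14 value on period plus the baseline value of the same variable, with an HC3 robust standard error and a 95% CI.
- Analyse lesion area on the square-root scale at both visits, fixed in advance. Area is a product of two lengths, so this returns it to a length scale and accepts zeros. Keep pain on its original scale.
- Keep the raw by-period summaries as descriptive, report the number of patients with both measurements, and label the result exploratory.

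The cost is a few lines of SAP text and two regressions in the Table 5.2 program. No new data are needed, since both variables are reported at both visits. The downside is that a patient lacking either measurement drops out of the adjusted estimate. A missing day 10-14 lesion measurement would be lost to the raw test as well under the observed-case rule in SAP 6.1.5.
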